8.1.1. Estimation of PK Parameters

PK parameters will be estimated by leveraging relevant PK data (ie, intensive PK data) using Phoenix WinNonlin® software (version 8.2.0) with standard noncompartmental methods. The linear up/log down rule will be used in conjunction with the appropriate noncompartmental model, with input values for dose level, dosing time, plasma concentration, and corresponding real-time values, based on drug dosing times whenever possible. If the PK scientist identifies that another method is more appropriate, the reasons for this decision should be documented.

All predose sample times before time-zero will be converted to 0.

Area under the curve (AUC) will be calculated, as appropriate, by the PK scientist. For AUC calculation, samples that are BLQ occurring prior to the achievement of the first quantifiable concentration will be assigned a concentration value of zero to prevent overestimation of the initial AUC. Samples that are BLQ at all other time points will be treated as missing data in WinNonlin®. The nominal time point for a key event or dosing interval (τ) may be used to permit direct calculation of AUC over specific time intervals. The appropriateness of this approach will be assessed by the PK scientist on a profile-by-profile basis.

Pharmacokinetic parameters such as AUC_{tau} , λ_z and $t_{1/2}$ (as applicable) are dependent on an accurate estimation of the terminal elimination phase of drug. The appropriateness of calculating these parameters will be evaluated upon inspection of PK data on a profile-by-profile basis by the PK scientist.

8.1.2. PK Parameters

PK parameters will be generated for all participants for whom parameters can be derived in the PK Analysis Set. The analyte presented in Table 8-1 will be evaluated if data are available.

Table 8-1. Study Treatments and Associated Analyte

GS-6212 Cohort	Treatment	Analyte
All GS-6212 Cohorts	GS-6212	GS-6212

The analyte and parameters presented in Table 8-2 will be used to evaluate the PK objectives of the study, as appropriate. The PK parameters to be estimated in this study are listed and defined in the PK Abbreviations section.

Table 8-2. PK Parameters for Each Analyte

Analyte	Parameters
GS-6212	For intensive PK sampling up to 12 hours postdose on Day 1 and Day 10, following parameters will be calculated (as applicable): AUC _{0-t} , AUC _{last} , AUC _{tau} , C _{max} , C _t , C _{last} , C _{tau} , C _{avg} , T _{max} , T _{last} , and additionally λ_z , CL/F, t _{1/2} , and V _z /F if applicable; accumulation ratio (Day 10 / Day 1) for Ct, C _{max} , AUC _{0-t} , and AUC _{last} ; C _{trough} on Day 11; C _{trough,avg} (average C _{trough} based on all predose trough sampling done across several days- D2, D3, D4, D7, D8, D9, D10, and D11)

8.2. Statistical Analysis Methods

8.2.1. General considerations

Individual participant concentration data and individual participant PK parameters for GS-6212 will be listed and summarized using descriptive statistics. Summary statistics (number of participants, mean, SD, coefficient of variation [%CV], median, min, max, Q1, and Q3) will be presented for both individual participant concentration data by visit/time point and individual participant PK parameters (as applicable). Moreover, the geometric mean, 95% CI, %Geometric CV [%GCV], and the mean and SD of the natural log-transformed values will be presented for individual participant PK parameter data.

Individual concentration data listings and summaries will include all participants with concentration data. The sample size for each time point will be based on the number of participants with nonmissing concentration data at that time point. The number and percentage of participants with concentration BLQ, as well as an indicator if more than one-third of the participants are BLQ will be presented for each time point. For summary statistics, BLQ values will be treated as zero at predose and postdose time points. If more than one-third of the values at a postdose time point are BLQ then the mean and SD will not be presented at that time point Concentration values will be presented as received from the bioanalytical lab and summary statistics will be presented to three significant digits.

8.2.2. PK Analyses

Individual PK parameter data listings and summaries will include all participants for whom PK parameter(s) can be derived. The sample size for each PK parameter will be based on the number of participants with nonmissing data for that PK parameter. Data and summary statistics will be presented to three significant digits.

The following tables will be provided for GS-6212:

- Individual estimates and summary statistics of plasma pharmacokinetic parameters on Day 1 and Day 10
- Individual data and summary statistics of plasma concentration (ng/mL) at protocol-specified sampling times
- Statistical comparisons of plasma pharmacokinetic parameter estimates on Day 10 vs Day 1 for the accumulation analysis

Accumulation analysis of analyte GS-6212 will be evaluated by comparing the relevant Day 10 PK parameters to Day 1 PK parameters within cohort 1. The analytes and parameters are presented in Table 8-3.

A mixed effects model with the natural log-transformed PK parameter as the dependent variable, a fixed effect for day, and a random effect for participant, will be used to estimate the difference between Day 10 and Day 1. A 90% CI for the true difference on the log-scale across all participants will be estimated. The estimate and associated 90% CI will be exponentiated to obtain an estimate of the GLSM ratio and its associated 90% CI.

The following SAS® PROC MIXED code will provide assessment for accumulation ratio for natural-log transformed parameters.

```
proc mixed;
where analyte='GS-6212 and paramed='parameter';
class subjid day;
random subjid;
model lnest = day / ddfm=kr;
lsmeans day / diff cl alpha = 0.1;
estimate 'Test (Day 10) versus Reference (Day 1)' day -1 1 / cl alpha = 0.10;
ods output Estimates = LS_Diffs LSMeans = LS_Means CovParms = MSE;
run;
```

Table 8-3. Analytes and PK Parameters for Estimation of Accumulation Ratios

Analytes	PK Parameters on Day 1	PK Parameters on Day 10
GS-6212	AUC _{0-8h} , AUC _{last} , C _{8h} , C _{max}	AUC _{0-8h} , AUC _{last} , C _{8h} , C _{max}

The following figures will be provided for GS-6212:

- Mean $(\pm SD)$ concentration data on Day 1 (on linear and semilogarithmic scales).
- Mean (± SD) concentration data on Day 10 (on linear and semilogarithmic scales).

• Mean (± SD) concentration data from Day 1 through Day 11 (on linear and semilogarithmic scales).

If more than one-third of the values at a postdose time point are BLQ, then the mean and SD will not be presented at that time point and remaining points connected. If lower error bar (mean-SD) is < 0 at a timepoint then it will not be presented at that timepoint.

- Median (Q1, Q3) concentration data on Day 1 (on linear and semilogarithmic scales).
- Median (Q1, Q3) concentration data on Day 10 (on linear and semilogarithmic scales).
- Median (Q1, Q3) concentration data Day 1 through Day 11 (on linear and semilogarithmic scales).

If more than one-third of the values at a postdose time point are BLQ then the median, Q1 and Q3 will not be presented at that time point and remaining points connected. If lower error bar (Q1) is BLQ at a timepoint then it will be presented as LLOQ at that timepoint.

• Individual participant concentration data versus time (on linear and semilogarithmic scales). Values of BLQ will be displayed as 0 on the linear scale and missing on the semi-logarithmic scale.

The following listings may be provided, as applicable:

• Plasma PK sampling details by participant, including procedures, differences in scheduled and actual draw times, and sample age

8.2.3. PK/PD Analyses

No formal PK/PD analysis is planned due to small number of participants in this study.

8.3. Sensitivity Analysis

Sensitivity analysis may be conducted for the key PK analyses if the PK scientist identifies PK data as questionable. The sensitivity analysis will exclude specific data from analyses, if appropriate. If a sensitivity analysis is deemed necessary, a listing of the PK parameter(s) data being excluded, with associated reason(s) provided by the PK scientist, will be generated.

10. SOFTWARE

 SAS^{\circledR} Software, SAS Institute Inc., Cary, NC, USA.

nQuery, Statsols, Cork, Ireland.

Phoenix WinNonlin® software, Certara, Radnor, PA, USA

11. SAP REVISION

Revision Date (DD MMM YYYY)	Section	Summary of Revision	Reason for Revision			

12. APPENDICES

Appendix 1. Study Procedures Table

Study Procedure	Screeninga	D1b	D2	D3	D4	D 7	D8	D9	D10	D11b	D25	ETc
Visit Window											±2D	
Written informed consent	X											
Medical history and demography	X											
Complete physical examination	X	X									X	X
Symptom-driven physical examination ^d			X		X	X				X		
Height	X											
Weight	X	X		X		X				X	X	X
Vital signse	X	X	X	X	X	X				X	X	X
HBV blood panel and HCV serology ^f	X											
CD4 cell count ^f	X	X								X	X	X
Plasma sample for HIV-1 genotyping/phenotyping ^{f,g}	X	X								Х		
Plasma HIV-1 RNAf	X	X	X	X	X	X	X	X	X	X	X	X
Hematology ^f	X	X		X		Х				X	X	X
Coagulation panelf	X	X				X				X	X	X
Chemistry ^f	X	X		X		X				X	X	X
Urinalysis ^f	X	X		X		X				X	X	X
Serum pregnancy test ^{f,h}	X											
Urine pregnancy test ^{fh,i}		X									X	X
Serum FSH ^{fj}	X											
12-Lead ECG	X	X				X				X	X	X
Intensive plasma PKk		X							X			
Single trough plasma PK ¹			X	X	X	X	X	X		X		X
Review AEs and concomitant medications ^m	X	X	X	X	X	Х	X	X	X	X	X	X
Study drug (GS-6212) dispensation ⁿ		X										
Study drug (GS-6212) dosing ^{o, p}		X	X	X	X	X	X	X	X			
BVY dispensation, as applicable										X		

Study Procedure	Screening ^a	D1 ^b	D2	D3	D4	D 7	D8	D9	D10	D11b	D25	ET
Visit Window											±2D	
BVY or an alternative SOC administration										Xq	őř	-

AE = adverse event; AM = before noon; BVY = bictegravir/emtricitabine/tenofovir alafenamide (B/F/TAF; coformulated; Biktarvy®); CD4 = clusters of differentiation 4; D = Day; ECG = electrocardiogram; eCRF = electronic case report form; ET = early termination; FSH = follicle-stimulating hormone; HBV = hepatitis B virus; HCV = hepatitis C virus; HIV-1 = human immunodeficiency virus type 1; PK = pharmacokinetic(s); RNA = ribonucleic acid; SAE = serious adverse event; SOC = standard of care

- a Prospective participants should be screened no more than 28 days prior to administration of the first dose of study drug.
- b Overnight fasting (≥ 6 hours prior to dosing) is required.
- c ET assessments will be performed within 72 hours of prematurely discontinuing from the study or study drug, as applicable.
- d Symptom-driven physical examinations will be performed as needed, based on reported signs and symptoms.
- e Vital signs include blood pressure, heart rate, respiration rate, and body temperature. Participants should be sitting down for 5 minutes before vital sign measurements are obtained.
- f See detailed list of laboratory assessments in Section 6.3.7 of the master protocol.
- Participants who meet the criteria for virologic failure at Day 11 will be tested for the potential development of resistance against all components of the treatment regimen, including the study drug. See Section 6.3.9.1.3 of the master protocol for management of virologic failure.
- h Participants assigned female at birth and of childbearing potential only.
- i A negative urine pregnancy test is required prior to study drug dosing on Day 1. Positive urine pregnancy tests will be confirmed with a serum test.
- j A serum FSH test is required for participants assigned female at birth who are younger than 54 years, not on hormonal contraception, and who have stopped menstruating for ≥ 12 months but do not have documentation of ovarian hormonal failure.
- k Intensive PK samples should be collected at these time points for all cohorts (relative to AM dosing): predose (\$\leq\$ 30 minutes before dose), 0.25, 0.5, 1, 2, 3, 4, 6, 8, and 12 hours postdose (\$\leq\$ 1 and 10). Please note that the 12-hour postdose sample (if collected) on Days 1 and 10 should be sampled prior to the administration of the PM dose, as applicable.
- 1 Single trough PK sample should be drawn prior to AM drug dosing (as applicable) on the indicated dosing days (ie, Days 2, 3, 4, 7, 8, 9, and 11).
- m From the time of obtaining informed consent through the first administration of study drug, record all SAEs, as well as any nonserious AEs related to protocol-mandated procedures, on the AE eCRF. All other untoward medical occurrences observed during the screening period, including exacerbation or changes in medical history are to be captured on the medical history eCRF. See Section 7, Adverse Events and Toxicity Management, for additional details.
- n Study drug bottles of GS-6212 will be dispensed on Day 1 (see Section 5.2.4).
- o For Cohort 1, a 100-mg dose of GS-6212 will be administered twice daily (ie, once every 12 hours ± 1 hour) on Days 1 through 10 (for further details on dosing and meal requirements, see Section 5.2.4). Subsequent cohort doses, dosing regimens, meal requirements (fasted or fed), and progression between cohorts will be adaptive and determined as summarized in Section 3.1.1.
- p Participants will take their study drug doses at home on Days 5 and 6.
- q After assessments on Day 11 or upon ET, participants will initiate a regimen of BVY provided by the sponsor or an alternative SOC ART regimen selected by the investigator. Participants who discontinue study drug before Day 11 should start this regimen at the time of discontinuation (see Section 6.4.1 of the master protocol).

Appendix 2. Details for Statistical Programming

For continuous HIV-1 RNA endpoints change from baseline on Day 11, and maximum change from Day 2 to Day 11, pairwise comparisons between GS-6212 cohort and historical placebo group will be performed and p-values will be presented.

The following SAS code will be used to generate p-values:

```
**Assign treatment groups for testing**;
data trtgrp;
set trtgrp;
   if dose ='100 mg' and meal='Fasted' then trt=1;
   else if treatment='Placebo' then trt2;
run;

ods output estimates=estimate;
proc mixed data = trtgrp;
class trt;
model chg = trt / ddfm=kr;

/*least squares means*/
lsmeans trt / diff e;

/* p-values */
estimate 'Cohort 1 vs Placebo' trt 1 -1 / cl alpha=0.05;
run;
```

GS-US-544-5905-03_SAP ELECTRONIC SIGNATURES

Signed by	Meaning of Signature	Server Date (dd-MMM- yyyy hh:mm:ss)
PPD	Biostatistics eSigned	28-Aug-2024 03:56:43
PPD	Project Team Leader eSigned	28-Aug-2024 16:23:03
PPD	Clinical Pharmacology eSigned	28-Aug-2024 16:42:19

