1.3. Sample Size and Power

A sample size of 6 to 8 participants in each dose cohort will provide 83% to 94% power to detect a treatment difference of $1.0 \log_{10} \text{copies/mL}$ in change from baseline in HIV-1 RNA on Day 11 between at least one of the study drug dose groups and the historical placebo group (N = 21). In this power analysis, it is assumed that a standard deviation (SD) for the change from baseline in

HIV-1 RNA on Day 11 is 0.662 log₁₀ copies/mL for each study drug dose group and 0.359 log₁₀ copies/mL for the placebo group, and a 2-sided t-test is conducted at an alpha level of 0.05. Standard deviations were estimated from historical Phase 1b studies conducted by the sponsor (GS-US-120-0104, GS-US-141-1219, and GS-US-200-4072). The maximum SD from treatment groups was used for the study drug dose group and SD from the pooled placebo group was used for the placebo group.

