6. EFFICACY ANALYSES

6.1. Primary Efficacy Endpoint

The primary efficacy endpoint is the change from baseline in plasma HIV-1 RNA (log₁₀ copies/mL) on Day 11.

Historical HIV-1 RNA data for placebo participants from 3 sponsor Phase 1b studies (GS-US-120-0104, GS-US-141-1219, and GS-US-200-4072) will be combined to form a single placebo group for the purpose of HIV-1 RNA analysis through Study Day 11. For Study GS-US-200-4072, HIV-1 RNA (log₁₀ copies/mL) collected on Day 10 will be used for "Day 11" since HIV-1 RNA was not collected on Day 11 for this study. GS-6212 cohort will be compared to the pooled placebo group with respect to the primary efficacy endpoint, the change from baseline in plasma HIV-1 RNA (log₁₀ copies/mL) on Day 11, using the 2-sided t-test conducted at an alpha level of 0.05. The analysis will be conducted using the FAS.

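### The Appendix 2 code runs an equal-variance t-test on the primary endpoint, but the SAP's own planning SDs are unequal and put its nominal 5% error at about 13% to 16%

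*SAP*

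**What the plan says.** - **Section 1.3** assumes that the SD of the Day 11 change "is 0.662 log₁₀ copies/mL for each study drug dose group and 0.359 log₁₀ copies/mL for the placebo group". It says that "A sample size of 6 to 8 participants in each dose cohort will provide 83% to 94% power" for a difference of 1.0 log10 copies/mL against 21 historical placebo participants, and that "a 2-sided t-test is conducted at an alpha level of 0.05". It adds that 0.662 is the largest SD seen in the historical treatment groups.
- **Section 6.1** compares the GS-6212 cohort with pooled placebo "using the 2-sided t-test conducted at an alpha level of 0.05". It does not say whether the variances are pooled or separate.
- **Appendix 2** gives the SAS code for the p-values on Day 11 change and on maximum change. The model is "model chg = trt / ddfm=kr", with treatment as the only effect and neither a RANDOM nor a REPEATED statement. The ESTIMATE statement also requests the 95% confidence interval.
- **Sections 6.2.1, 6.3 and 6.4** apply the primary-endpoint method to Day 8, to maximum reduction and to the sensitivity analyses of Day 11 change and maximum reduction.

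**The concern.** Without a GROUP= option, PROC MIXED estimates one residual variance for both arms. The Kenward-Roger option does not help, because it adjusts degrees of freedom for the covariance model that was fitted. With a single residual variance it returns n1 + n2 − 2, which is 25 to 27 here. The code is therefore the classical pooled t-test.

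That test is safe against unequal variances only when the groups are of similar size. Here the group assumed to be more variable has 6 to 8 participants and the less variable one has 21. The pooled variance is then dominated by the placebo group, and the standard error comes out too small. At stake are the level of the primary test, the honesty of its confidence interval, and whether the power statement belongs to the test being run.

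**Working it through.** **Inputs (Section 1.3):** s1 = 0.662 (GS-6212, n1 = 6 to 8); s2 = 0.359 (placebo, n2 = 21); difference 1.0; two-sided alpha 0.05.

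**Step 1: reproduce the stated power with the unequal-variance test.**

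SE = sqrt(s1²/n1 + s2²/n2), with Satterthwaite df = (s1²/n1 + s2²/n2)² / [(s1²/n1)²/(n1−1) + (s2²/n2)²/(n2−1)].

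- n1 = 6: SE = sqrt(0.4382/6 + 0.1289/21) = 0.281; df = 5.87; noncentral-t power 83.6% (simulated 83.2%).
- n1 = 8: SE = sqrt(0.4382/8 + 0.1289/21) = 0.247; df = 8.62; power 94.6% (simulated 94.4%).

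Both ends agree with the stated 83% to 94%. The alternatives tried do not match both ends:

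| Method | n1 = 6 | n1 = 8 |
|---|---|---|
| Pooled t-test as coded (simulated) | 97.9% | 99.2% |
| Unequal-variance SE with n1 + n2 − 2 df | 92.7% | 97.4% |
| Normal approximation, unequal SDs | 94.5% | 98.2% |
| Common SD of 0.662 | 90.4% | 95.3% |

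**Step 2: the standard error used by the code.**

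Pooled SD = sqrt{[(n1−1)s1² + (n2−1)s2²]/(n1+n2−2)}; pooled SE = pooled SD × sqrt(1/n1 + 1/n2).

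- n1 = 6: sqrt[(5 × 0.4382 + 20 × 0.1289)/25] = 0.437; SE = 0.437 × sqrt(1/6 + 1/21) = 0.202. True SE 0.281, ratio 1.39.
- n1 = 8: pooled SD 0.457; SE = 0.190. True SE 0.247, ratio 1.30.

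**Step 3: type I error.** A quick approximation is 2Φ(−1.96 × pooled SE / true SE), which gives 15.9% at n1 = 6 and 13.1% at n1 = 8. Simulation with normal data, zero true difference and 1,000,000 trials per case gives:

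| n1 | Pooled (as coded) | Welch |
|---|---|---|
| 6 | 15.6% | 5.4% |
| 7 | 14.2% | 5.3% |
| 8 | 13.0% | 5.2% |

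Coverage of the coded 95% interval is 100% minus these figures: about 84%, 86% and 87%. For normal data this shortfall does not depend on the true difference.

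**Step 4: dependence on the GS-6212 SD (pooled test, n1 = 6, placebo SD 0.359).** The error is about 12.0% at an SD of 0.55, 10.0% at 0.50, 8.2% at 0.45, 5.0% at 0.359, and about 1% at 0.20. The Welch test stays between 4.9% and 5.5% across these cases.

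**The case against.** The strongest reply is that 13% to 16% is a worst case.

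- **The SD is a maximum.** The 0.662 was a cautious sample-size input, and a smaller true SD brings a smaller inflation, as Step 4 shows. This stands: the figure is conditional on the planning SDs.
- **The null scenario is unusual.** If the drug did nothing, its recipients might vary much as placebo recipients do, and the pooled test would then hold 5.0%. This is fair for the p-value, although the controls are historical and come from other studies, so equal spread is not assured even then. It does not rescue the confidence interval, which under-covers at any true effect if the treated group is more variable.
- **The conclusion may not change.** At a 1.0 log10 difference and the planning SDs, Welch rejects in 83% to 94% of trials and the pooled test in 98% to 99%. At 1.5 log10 both reject in at least 99%. This also stands: the tests differ mainly for smaller effects and in interval width.
- **The cohort could be larger than 8,** since Section 1.2 sets only a minimum of 6. At an SD of 0.662 the error is still 11.0% with 10 participants and 9.4% with 12.
- **It is a proof-of-concept study,** and Section 2.2 records that no further cohorts followed. Section 3.5 uses that status to waive multiplicity adjustment. It does not waive the level of the single primary test, which Sections 2.3 and 6.1 fix at 0.05.

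Section 3.7 allows transformed or nonparametric analysis when normality is inadequate. It does not address unequal variances.

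**Conclusion.** The concern holds. The code in Appendix 2 is the equal-variance test, and the power in Section 1.3 was evidently computed for the unequal-variance test. That mismatch is a matter of arithmetic and does not depend on the data eventually observed.

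Under the SAP's own SDs, normal data and 6 to 8 treated participants, the nominal 5% test runs at 15.6% to 13.0%, and the nominal 95% interval covers about 84% to 87%. The size of the error rests on the variance ratio: none if the SDs are equal, about 8% at a treated SD of 0.45 with 6 participants, and over-conservative if the treated group is the less variable one. Section 6.1 is incomplete rather than wrong; the fault lies in the code that produces the p-value and interval. It should be corrected before the primary analysis is relied on.

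**What to change.** In Appendix 2, add `repeated / group=trt;` after the MODEL statement, with Satterthwaite or Kenward-Roger degrees of freedom, or take the Satterthwaite row of PROC TTEST. In Section 6.1, name the test as a two-sided unequal-variance (Welch) t-test. State that it also applies to Day 8, maximum reduction and the tested analyses in Section 6.4, where exclusions may shrink the treated group further. If the SAP is already final, document the change in the study report, as Section 1 requires.

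The cost is one line of code and one phrase. At the planning SDs with 6 participants, the median half-width of the 95% interval rises from about 0.41 to 0.65 log10, and power at 1.0 log10 falls from 97.9% to the stated 83%; the higher figure was obtained at an inflated error rate. With equal SDs the Welch error rate is 5.4% at n = 6 and 5.1% at n = 8.

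The same code block needs one other repair: the statement that assigns the placebo group lacks its equals sign and is not a valid assignment.
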